Statistical Analysis Plan

Ref: SAP001V04

TRIHEP 3

A comparative phase 2 study assessing the efficacy of triheptanoin, an anaplerotic therapy in Huntington’s Disease

Sponsor Inserm n°: C14-62

Coordinating Investigator: [name]
Département de Génétique
ICM UPMC, Inserm UMR_S1127/CNRS
UMR 7225

[name] Biostatistician	[name] Reviser position:	[name] Approver’s position:
Date : 09/ 01/2019 (DD/MM/YYYY)	Date : 09/01/2019 (DD/MM/YYYY)	Date : 09/01/2019 (DD/MM/YYYY)
Signature :	Signature	Signature :

ABBREVIATIONS

31P-MRS	31-Phosphorus Magnetic Resonance Spectroscopy (³¹ P-MRS)
ANOVA	Analyse of Variance
ANCOVA	Analyse of Covariance
CAG	Cytosine-Adenine-Guanine Cr = Creatine
HD	Huntington's disease
HTT	Huntingtin
MRI	Magnetic Resonance Imaging
PBA-S	Problem Behavior Assessment Short version
PCr	Phosphocreatine
Pi	inorganic Phosphate
SAP	Statistical Analysis Plan
SDMT	Symbol Digit Modality Test
SF-36	Short Form 36
TFC	Total Functional Capacity
TMT	Trail Making Test
UHDRS-TMS	Unified Huntington's Disease Rating Scale Total Motor Score

SAP001V04/TRIHEP3

Last date of modification: 09/01/2019

Biostatistician: [name]/[name]

SAP001V04/TRIHEP3	Date of modification: 09/01/2019
	Biostatistician: [name]/[name]

POP_TE116	Effective on: 09/01/2019	Version: 04
-----------	--------------------------	-------------

1 History of modifications

Version	Author	Modification description	Date
V01	[name]	Draft SAP creation	08/10/2018
V02	[name]	Revision	02/01/2019
V03	[name]	Edits	06/01/2019
V04	[name]	Finalization	09/01/2019

SAP001V04/TRIHEP3

Last date of modification: 09/01/2019

Biostatistician: [name]/[name]

2 Introduction

This Statistical Analysis Plan (SAP) is prepared by the URC Lariboisiere for a 2 centers, randomized, double-blind, placebo-controlled study (the TRIHEP3 Trial) to evaluate the benefit of triheptanoin in early affected HD patients compared to placebo, the study entitled: A comparative phase 2 study assessing the efficacy of triheptanoin, an anaplerotic therapy in Huntington's Disease (Project Code: C14-62, ClinicalTrials.gov Identifier: NCT02453061, EUDRACT No.: 2014-005112-4).

The primary objective of this clinical trial is to assess the efficacy of triheptanoin compared to placebo in decreasing of the caudate volume using volumetric magnetic resonance imaging.

The specific structure and content of SAP meets the requirements of the State Food and Drug Administration's biostatistical technical guidelines for clinical trials of chemical drugs and biological products and the technical requirements of ICH on drug registration.

This document describes the statistical analysis plan (SAP) for the TRIHEP3 trial and includes more detailed procedures for executing the statistical analyses of the primary and secondary endpoints. This SAP is based on the protocol version 7.0 (Dated 7 January 2019) and finalized before patient enrolment is completed and the database is locked for analysis. This SAP was written by the trial statistician and principal investigator and approved by the Head of biometry. All changes to the statistical analyses planned in the trial protocol are documented in Section 10.

3 Study objectives and endpoints

3.1 Hypothesis

Our proof-of-concept study strongly suggests that triheptanoin is able to improve the brain metabolic profile of HD patients at an early stage of the disease. It is very unlikely that these changes in brain energy metabolism are observed by chance as we have previously validated that the Pi/PCr changes in HD patients are stable over time, including over a one-month interval. Of note, the correction of the Pi/PCr response during brain activation was particularly notable when compliance to triheptanoin was ensured. We also observed an interesting trend of improved motor functions in HD patients after one month of anaplerotic therapy although these findings have to be interpreted with caution due to a possible placebo effect in this open-label study.

Thanks to neuroimaging biomarkers already validated in HD and the newly identified metabolic brain biomarkers using ³¹phosphorous magnetic resonance spectroscopy (MRS), we can test for a reduction in neurodegeneration among HD patients resulting from an improvement in brain energy profiles with triheptanoin.

SAP001V04/TRIHEP3

Last date of modification: 09/01/2019

Biostatistician: [name]/[name]

In our follow-up study, TRIHEP 3, we plan to include 100 early affected HD patients ($5 \leq \text{UHDRS} \leq 40$) in a randomized, double-blind, controlled study in 2 centers (France and the Netherlands). Patients will receive either triheptanoin at 1g/kg of body weight per day ($n = 50$), or a control oil ($n = 50$) for 6 months followed by an open label phase using triheptanoin for another 6 months. Efficacy of triheptanoin will be evaluated by measurements of caudate volume using volumetric magnetic resonance imaging and brain energy metabolism as evaluated by the ratio of inorganic phosphate/phosphocreatine, during visual stimulation, using ^{31}P -MRS. Clinical improvement will be evaluated by UHDRS, TFC, and PBA-S score as well as performance on the neurocognitive battery; patient quality of life will be evaluated with the SF-36 questionnaire before and after treatment; biological tolerance and compliance will be evaluated by routine biochemical blood tests, plasma and urine measurements of triheptanoin oil derivatives and patient report.

3.2 Principal objective

The primary objective of TRIHEP 3 is to evaluate the efficacy of triheptanoin in slowing atrophy in the caudate of early affected HD patients as measured with volumetric magnetic resonance imaging.

3.3 Secondary objective(s)

The secondary objectives are:

- To assess the efficacy of triheptanoin in restoring brain energy profiles using ^{31}P phosphorous spectroscopy, and in slowing white matter alterations using diffusion tensor imaging.
- To assess the clinical benefit of triheptanoin on motor function in HD patients using scores on the United Huntington's Disease Rating Scale.
- To assess the clinical benefit of triheptanoin on psychiatric symptoms and cognitive function in HD patients using scores on the PBA-S, SDMT, TMT, Digit span test and Stroop test.
- To assess the effect on quality of life (SF-36) of HD patients of therapeutic use of triheptanoin.
- To confirm long-term clinical and biological tolerance of triheptanoin in HD patients.

SAP001V04/TRIHEP3

Last date of modification: 09/01/2019

Biostatistician: [name]/[name]

3.4 Primary endpoint

The primary efficacy endpoint is the change from baseline to 6 months in caudate atrophy as measured by caudate boundary shift integral (cBSI).

3.5 Secondary endpoints

- Change from baseline to 3, 6 and 12 months in index of brain energy restoration (defined as delta of activation-recovery from the Pi/PCr ratio measured by ³¹phosphorous MRS).
- Change from baseline to 12 months in caudate atrophy as measured by cBSI.
- Change from baseline to 6 and 12 months in DTI metrics and fiber integrity as measured by FBA.
- Change from baseline to 6 and 12 months in TMS and TFC.
- Change from baseline to 6 and 12 months in PBA-s, SDMT, TMT, Digit-Span, Stroop and SF-36.

3.6 Safety endpoints

Safety and long-term tolerance of Triheptanoin based on review of adverse events and changes in clinical labs and physical examination/vital signs.

4 Experimental plan

4.1 Study design

TRIHEP3 is a phase 2a, multicenter, double-blind, randomized, controlled two-armed study evaluating the efficacy of 1g/kg of body weight triheptanoin per day versus a placebo for a six-month treatment period, followed by a 6-month open-labelled period with all patients treated with triheptanoin.

4.2 Measures to limit bias

Double-blind, randomized design.

SAP001V04/TRIHEP3

Last date of modification: 09/01/2019

Biostatistician: [name]/[name]

5 Number of necessary subjects

The rate of progression of caudate atrophy is linear in HD patients at an early-disease stage (Tabrizi SJ, Scahill RI, Owen G, et al. Predictors of phenotypic progression and disease onset in premanifest and early-stage Huntington's disease in the TRACK-HD study: analysis of 36-month observational data. *Lancet Neurol.* 2013;12(7):637-649). We hypothesized that, in patients under placebo, the progression of caudate atrophy over 6 months would be reduced by 42%. Based on such hypothesis and data from the TRACK-HD study, fifty patients under placebo and fifty patients treated with triheptanoin would be required to achieve 80% power at the one-sided 0.025 alpha level. Therefore, a total of 100 patients was required.

6 Study population

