6.3 Population to analyze

Intent-to-treat (ITT) Population

The main efficacy analysis will be based on all data in the intention-to-treat population defined as all randomized patients who have signed an informed consent form. In case of consent withdrawal, only data collected before withdrawal will be used. All patients will be analyzed on the basis of their randomized group of treatment.

Per-Protocol (PP) Analysis Set

In addition, an explanatory analysis (PP) of all patients randomized and treated without major protocol violations/deviations will be carried out. Pre-defined major protocol violations/deviations are:

1. Missing data for the primary efficacy endpoints
2. Premature discontinuation of treatment, whatever the reason.
3. Unjustified change in treatment during follow-up
4. Inclusion in another clinical study

7 Variables measured and kept for analysis

All variables of the eCRF and those in additional files reporting data from MRI are kept for analysis. Regarding these latter following variables will be used:

- Index of brain energy restoration:

The delta of activation-recovery from the Pi/PCr ratio measured by ³¹phosphorous MRS will be taken as the index of brain energy restoration.

- Caudate atrophy:

This will be the caudate volume loss (proportion of baseline volume) as measured by the caudate boundary shift integral (cBSI).

- Diffusion tensor metrics:

Fractional anisotropy (FA), radial diffusivity (RD), mean diffusivity (MD).

- Fiber tracking metrics:

Fiber density (FD), fiber cross-section (FC) and a combination of both - fiber density and cross-section (FDC).

SAP001V04/TRIHEP3

Last date of modification: 09/01/2019

Biostatistician: [name]/[name]

Diffusion tensor metrics and fiber tracking metrics will be analyzed in the following areas from the JHU-atlas:

- Middle cerebellar peduncle
- Pontine crossing tract
- Genu of corpus callosum
- Body of corpus callosum
- Splenium of corpus callosum
- Fornix
- Corticospinal tract
- Medial lemniscus
- Inferior cerebellar peduncle
- Superior cerebellar peduncle
- Cerebral peduncle
- Anterior limb of internal capsule
- Posterior limb of internal capsule
- Retrolenticular part of internal capsule
- Anterior corona radiata
- Superior corona radiata
- Posterior corona radiata
- Posterior thalamic radiation
- Sagittal stratum
- External capsule
- Cingulum (cingulate gyrus)
- Cingulum (hippocampus)
- Fornix (cres) / Stria terminalis
- Superior longitudinal fasciculus

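### Does Section 5 of the SAP overstate its power by making no allowance for losses, and does it put the 42% effect in the wrong arm?

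*SAP*

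**What the plan says.** Section 5 of the SAP gives the sample-size argument in one short paragraph. The effect assumption reads "We hypothesized that, in patients under placebo, the progression of caudate atrophy over 6 months would be reduced by 42" percent. The calculation is then introduced with "Based on such hypothesis and data from the TRACK-HD study", and the result is that "fifty patients under placebo and fifty patients treated with triheptanoin would be required to achieve 80% power at the one-sided 0.025 alpha level". The paragraph ends: "Therefore, a total of 100 patients was required". It gives no mean, no standard deviation and no loss rate.

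Section 3.1 uses the same total: "we plan to include 100 early affected HD patients", split 50 and 50. Section 3.2 states the principal objective as the efficacy of triheptanoin "in slowing atrophy in the caudate of early affected HD patients".

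On who is analysed, Section 6.3 says: "The main efficacy analysis will be based on all data in the intention-to-treat population defined as all randomized patients". It adds: "In case of consent withdrawal, only data collected before withdrawal will be used". The same section counts missing primary endpoint data as a major deviation for the per-protocol set. Section 8 plans multiple imputation for the main criterion. Section 9 calls the study mainly exploratory, sets a two-sided 5% level for the main criterion, and asks for the 95% confidence interval of the difference between groups.

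**The concern.** Two things catch the eye.

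First, the number required for 80% power equals the number to be included. The SAP expects that some month-6 caudate measurements may be missing, yet it shows no step from evaluable to randomised patients. On a plain reading, 80% then holds only if all 100 measurements are obtained. If some are lost, a non-significant primary result would be judged against a power a few points too high.

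Second, the only stated effect assumption says that atrophy will slow under placebo. Taken literally, this contradicts the trial's objective. A reader might ask whether the calculation was done for a different contrast from the one to be tested.

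**Working it through.** **Inputs from the SAP.** 50 per arm, 80% power, one-sided 0.025 and a 42% reduction (Section 5). Two-sided 0.05 for the main criterion, and an ANOVA without covariates as the primary model (Section 9). One-sided 0.025 and two-sided 0.05 use the same critical value, so the two statements of alpha agree.

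**Reproducing the stated figure.** A forward calculation is not possible, because neither the placebo mean nor the SD of the 6-month change is given. Only the standardised effect d implied by the stated figures can be found.

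- Normal approximation: d = (1.960 + 0.842) × √(2/50) = 2.802 × 0.2 = 0.560.
- Noncentral t, solving 1 − F(t(0.975, 98); 98, d√(50/2)) = 0.80: d = 0.566.

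Putting 0.560 back into the sample-size formula returns 50 per arm. That is circular: it shows that the figures are coherent, not that they are right.

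**If 50 means evaluable patients and losses are not recovered.** The loss rates below are assumptions, equal in both arms. Power uses the noncentral t with d = 0.566. The last column is 50/(1 − loss), rounded up.

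| Assumed loss | Evaluable per arm | Power | To randomise per arm for 80% |
|---|---|---|---|
| 5% | 47.5 | 0.779 | 53 |
| 10% | 45 | 0.756 | 56 |
| 15% | 42.5 | 0.732 | 59 |
| 20% | 40 | 0.705 | 63 |

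The normal approximation gives nearly the same powers: 0.780, 0.757, 0.733 and 0.707.

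**Compared with the unknown SD.** Read the 42% as a share of the placebo mean change. Then d = 0.42/(SD/mean), so 80% power at 50 per arm implies SD/mean = 0.42/0.566 = 0.742. If the true ratio lay anywhere from 0.6 to 1.0 (an assumed range), power at 50 per arm would run from 94% to 56%, and the required number from 33 to 89 per arm. Uncertainty of that kind outweighs the 2 to 9 points in the table.

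**Could the SD/mean ratio show which reading applies?** Not between no allowance and a small one. Take 42% as rounded, from 41.5% to 42.5%.

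- With 50 evaluable, the noncentral t gives 0.415/0.5659 = 0.733 to 0.425/0.5659 = 0.751.
- With a 5% allowance inside the 50 (47.5 evaluable), the normal approximation has d = 2.802 × √(2/47.5) = 0.575, which gives 0.722 to 0.739.

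The SAP does not name its method, so a ratio from 0.733 to 0.739 fits both readings.

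**The placebo wording.** In Section 5, atrophy is reduced in patients under placebo. In Section 3.2, triheptanoin is to slow it, and Section 3.1 likewise tests for less neurodegeneration with triheptanoin. Only one reading fits all three: a 42% reduction under triheptanoin relative to placebo. The two-group calculation depends on the size of the difference, the SD and the arm sizes, and the arms are equal. Naming the other arm changes none of these, and the ratios above already use the sensible reading.

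**The case for a change.** The strongest case for a change is that the SAP chose to restate the calculation and so should restate it properly. Its power figure can be read in two ways, imputation does not in general restore the information in a missing month-6 scan, and no protocol text can make the placebo sentence right. Two or three sentences would settle all of it.

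Most of this is true as description. The placebo sentence is wrong as written, the ambiguity is real, and the arithmetic on assumed losses is sound. What does not follow is that the plan is deficient. The mean, the SD, the loss rate and the meaning of 50 belong to the sample-size justification, which an SAP commonly leaves to its protocol. Sections 5 and 3.1 agree on 100. Provision for withdrawal and missing data is ordinary contingency text and does not contradict a power statement. Section 6.3 makes all randomised patients the main analysis population, which favours reading 50 as randomised, although it does not settle whether an allowance was built in. As for misjudging a null result, the confidence interval required by Section 9 will show the precision achieved, whatever power was planned.

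**Conclusion.** No change to the plan follows. The first point is an omission that the protocol may well fill. The SAP does not show that 100 patients or 80% power is wrong, and an allowance inside the 50 cannot be excluded. In the less favourable case, where 50 means evaluable and imputation recovers nothing, power would be about 78% at a 5% loss and 76% at 10%, falling to 71% at 20%. Those rates are assumptions, with equal loss and equal SD in both arms. Any information recovered by imputation would make the fall smaller. In a trial described as mainly exploratory, with the primary test, population and decision rule untouched, restating the power would gain nothing of substance.

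The second point is a genuine misstatement but a clerical one. Sections 3.1 and 3.2 leave no doubt about the intended direction, and no figure, test or conclusion depends on the slip. The sponsor could tidy the sentence, after confirming the intended meaning, whenever the document is next edited.

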6.1 Inclusion criteria

- Positive genetic test with CAG repeat length ≥ 39 in HTT gene
- At least 18 years of age
- Signature of informed consent
- Covered by social security
- UHDRS score between 5 and 40
- Ability to undergo MRI scanning

6.2 Non-inclusion criteria

- Hypersensitivity to triheptanoin or to one of its excipients
- Additional psychiatric or neurological conditions
- Severe head injury
- Participation in another therapeutic trial (3 months exclusion period)
- Pregnancy or breastfeeding
- Inability to understand information about the protocol
- Persons deprived of their liberty by judicial or administrative decision
- Adult subject under legal protection or unable to consent
- Treatment with tetrabenazine
- Neuroleptic treatments other than olanzapine at small doses (≤ 10 mg) and aripiprazole (≤ 15 mg)

SAP001V04/TRIHEP3

Last date of modification: 09/01/2019

Biostatistician: [name]/[name]

6.3 Population to analyze

Intent-to-treat (ITT) Population

The main efficacy analysis will be based on all data in the intention-to-treat population defined as all randomized patients who have signed an informed consent form. In case of consent withdrawal, only data collected before withdrawal will be used. All patients will be analyzed on the basis of their randomized group of treatment.

Per-Protocol (PP) Analysis Set

In addition, an explanatory analysis (PP) of all patients randomized and treated without major protocol violations/deviations will be carried out. Pre-defined major protocol violations/deviations are:

1. Missing data for the primary efficacy endpoints
2. Premature discontinuation of treatment, whatever the reason.
3. Unjustified change in treatment during follow-up
4. Inclusion in another clinical study

7 Variables measured and kept for analysis

All variables of the eCRF and those in additional files reporting data from MRI are kept for analysis. Regarding these latter following variables will be used:

- Index of brain energy restoration:

The delta of activation-recovery from the Pi/PCr ratio measured by ³¹phosphorous MRS will be taken as the index of brain energy restoration.

- Caudate atrophy:

This will be the caudate volume loss (proportion of baseline volume) as measured by the caudate boundary shift integral (cBSI).

- Diffusion tensor metrics:

Fractional anisotropy (FA), radial diffusivity (RD), mean diffusivity (MD).

- Fiber tracking metrics:

Fiber density (FD), fiber cross-section (FC) and a combination of both - fiber density and cross-section (FDC).

SAP001V04/TRIHEP3

Last date of modification: 09/01/2019

Biostatistician: [name]/[name]

Diffusion tensor metrics and fiber tracking metrics will be analyzed in the following areas from the JHU-atlas:

- Middle cerebellar peduncle
- Pontine crossing tract
- Genu of corpus callosum
- Body of corpus callosum
- Splenium of corpus callosum
- Fornix
- Corticospinal tract
- Medial lemniscus
- Inferior cerebellar peduncle
- Superior cerebellar peduncle
- Cerebral peduncle
- Anterior limb of internal capsule
- Posterior limb of internal capsule
- Retrolenticular part of internal capsule
- Anterior corona radiata
- Superior corona radiata
- Posterior corona radiata
- Posterior thalamic radiation
- Sagittal stratum
- External capsule
- Cingulum (cingulate gyrus)
- Cingulum (hippocampus)
- Fornix (cres) / Stria terminalis
- Superior longitudinal fasciculus
- Superior fronto-occipital fasciculus
- Uncinate fasciculus
- Tapetum

8 Missing data

For the main criterion a multiple imputation technic will be used in case of missing data (SAS PROC MI). No imputation will be used for secondary criteria.

SAP001V04/TRIHEP3

Last date of modification: 09/01/2019

Biostatistician: [name]/[name]

9 Statistical analysis

Tabulated descriptive statistics by treatment will be provided for all parameters recorded in the eCRF.

Analysis of Continuous Data:

Continuous variables will be summarized using number of observations, mean, standard deviation, minimum, maximum, 25%, 50%, 75% quantiles and the two-sided 95% confidence intervals. Means, medians, minimum, maximum and standard deviations will be presented to one further decimal place. In addition, 95% confidence interval of difference between groups will be reported. Exact confidence intervals will be used if required.

Analysis of Categorical Data:

There will be counting of the absolute and relative frequencies (percentages) for categorical variables. Percentages will be rounded to one decimal place and there may be occasions where the total of the percentages does not equal 100% exactly.

General considerations regarding alpha value:

The nature of this study is mainly exploratory. We identified a main criterion for which a 5% two-sided alpha value has been chosen for statistical inference. As regards to the secondary criteria, we did not adjust alpha value for multiplicity since all the statistical inference regarding these numerous criteria should be considered as exploratory.

General considerations regarding parametric or non-parametric procedures:

All variables will be checked for their gaussian distributions by Shapiro-Wilk 's test. In case of non-normality, a normalizing transformation will be used. If this procedure failed a rank analysis will be used.

Demographic and other baseline characteristics data will be summarized descriptively as described above and will be summarized using Consort standard tabulations and listings will be generated.

Disposition of patients, patient status and patients excluded from ITT, PP populations will be summarized by treatment group. Descriptive statistics for primary reason for patient's withdrawal will be also presented by treatment group as well as a list of these patients sorted by treatment group.

Primary endpoints:

The difference between the two groups regarding change from baseline in caudate atrophy at M6 will be analyzed using an ANOVA (SAS PROC MIXED) with Kenward-Roger's adjusted degrees of freedom. Adjusted analysis will be performed using ANCOVA with age, gender and BMI as covariates. Prior to performing statistical tests, the assumptions of normality and

SAP001V04/TRIHEP3

Last date of modification: 09/01/2019

Biostatistician: [name]/[name]

homogeneity of variances of residuals were tested using Shapiro-Wilk test and Levene's test respectively. If the data meet the normality assumption and do not meet homogeneity assumption, proc mixed allows to estimate separately the variance-covariance matrices in repeated statement using group option and thereby overcome the issue of heterogeneity of variance. If the data do not meet the normality or homogeneity assumptions of the parametric tests and are highly skewed, then a rank analysis was used.

Secondary criteria

- The difference between the two groups regarding change from baseline in index of brain energy restoration at M3, M6 and M12 (defined as delta of activation-recovery from the Pi/PCr ratio measured by ³¹phosphorous MRS) will be analyzed using ANCOVA with baseline value as covariate. Adjusted analysis will be performed using ANCOVA with baseline value, age, gender and BMI as covariates
- The difference between the two groups regarding change from baseline in caudate atrophy at 1 year will be analyzed using ANOVA. Adjusted analysis will be performed using ANCOVA with age, gender and BMI as covariates.
- Diffusion tensor metrics and fiber tracking metrics will be analyzed using ANCOVA.
- Clinical scores will be analyzed using ANCOVA with baseline value as covariates. Adjusted analyses will be performed using an ANCOVA with baseline value, age, gender and BMI as covariates.
- Long-term compliance will be confirmed by regular biochemical testing from blood and urine samples – especially the levels of plasma propionylcarnitine and urinary 3-hydroxypropionic, 2-methylcitric, propionylglycine, tiglylglycine and/or methylmalonic acid – as well as by oil container accounting at study visits. The number of patients with detectable levels of triheptanoin metabolites will be reported.
- In addition, specific image analysis will be performed by the imaging department to allow for voxel-wise statistical comparisons and visualization of significant brain areas. These voxel-wise analytical methods will include tract-based spatial statistics for the diffusion tensor metrics and connectivity-based fixel enhancement for the fiber tracking metrics.

Safety endpoints:

- Long-term tolerance will be confirmed by clinical exam at study visits and by patient report during phone calls and/or visits. Side effects will be described in both arms of the trial. All Severe Adverse Events will be described by group and body system.

SAP001V04/TRIHEP3

Last date of modification: 09/01/2019

Biostatistician: [name]/[name]

10 Changes to the statistical analyses planned in the protocol

The main analyses were described in the protocol version 4 (dated 7 January 2019) for the trial TRIHEP3. In the protocol version 3 (dated 1 June 2015), the two co-primary endpoints were caudate volume using volumetric magnetic resonance imaging, and brain energy metabolism as evaluated by the delta in Pi/PCr ratio between visual stimulation and recovery using ³¹phosphorous MRS. To avoid multiplicity issues, the caudate volume will be analyzed as primary endpoint and brain energy metabolism as secondary endpoint.

11 Software and Programs used

All hypotheses testing will be carried out at the 5% (two-sided) significance level and statistical analyses will be performed using SAS 9.4 software. Image analysis and visualization will be performed using FSL and MRtrix.

POP_TE116	Effective on: 09/01/2019	Version: 04
-----------	--------------------------	-------------

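### The 12-month cBSI comparison makes no use of the month-6 cBSI of patients without a month-12 scan, which costs precision and leaves it open to bias if dropout depends on month-6 atrophy differently by arm

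*SAP*

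**What the plan says.** The primary endpoint is cBSI at month 6 (Section 3.4), and Section 8 protects it: "For the main criterion a multiple imputation technic will be used in case of missing data (SAS PROC MI"). The same measure at month 12 is a secondary endpoint in Section 3.5: "Change from baseline to 12 months in caudate atrophy as measured by cBSI". For all secondary endpoints Section 8 says: "No imputation will be used for secondary criteria".

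Section 9 gives the 12-month test: "The difference between the two groups regarding change from baseline in caudate atrophy at 1 year will be analyzed using ANOVA". The adjusted version adds only demographic and body-size terms: "Adjusted analysis will be performed using ANCOVA with age, gender and BMI as covariates". Month-6 cBSI is in neither model. PROC MIXED and its repeated statement are mentioned only for the month-6 primary analysis, the latter to allow unequal variances.

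The Pi/PCr index, analysed as "change from baseline in index of brain energy restoration at M3, M6 and M12", and the clinical scores are given ANCOVA with the baseline value. No secondary model includes an earlier post-baseline visit. Section 6.3 keeps data collected before a withdrawal of consent, so a month-6 scan from a patient who leaves later can be used.

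**The concern.** Ruling out imputation is not a fault in itself, since a likelihood-based repeated-measures model needs none. The weakness is the combination of no imputation with a test that looks at month 12 alone. In practice that is an available-case comparison, although the SAP does not use the term.

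Section 7 defines caudate atrophy as volume lost as a proportion of baseline, so 12-month loss contains 6-month loss and the two should be well correlated. For a patient who misses the month-12 scan, the best available predictor of the missing value has already been collected, and the plan leaves it out. Two things follow. The 12-month estimate is less precise than it could be. It also moves away from the true difference if the patients who leave are selected on month-6 atrophy to a different extent in the two arms.

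**Working it through.** **Inputs.** From the SAP: 50 patients per arm (Section 5). The SAP gives no dropout rate, no month-6 to month-12 correlation and no figure for the 12-month analysis, so there is no stated result to reproduce. Assumed, as ranges: proportion missing month 12 after a month-6 scan, p = 0.10 to 0.20; correlation ρ = 0.6 to 0.9; and, where dropout depends on month-6 loss, a log-odds slope b = 0.5 to 1 per SD. Results are in SD units of 12-month cBSI.

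**Precision under random dropout.** Per arm:

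- Available-case mean: variance = σ² / [n(1 − p)].
- Likelihood mean using month 6: variance = σ² [(1 − ρ²) / (n(1 − p)) + ρ² / n].
- Ratio of the second to the first = 1 − pρ², so the proportional saving is pρ².

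Low end: 0.10 × 0.6² = 3.6%. High end: 0.20 × 0.9² = 16.2%. With 20% missing, 40 month-12 scans per arm carry the information of 40 / 0.928 = 43 scans at ρ = 0.6, or 40 / 0.838 = 48 at ρ = 0.9.

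**Bias when dropout depends on month-6 loss in one arm only.** Let π be the logistic dropout probability, with mean p over a standard normal month-6 value. The mean month-6 value among those who stay is −b·E[π(1 − π)] / (1 − p), and the 12-month mean in that arm shifts by ρ times this amount.

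- Low end (p = 0.10, b = 0.5, ρ = 0.6): E[π(1 − π)] = 0.0879 by numerical integration; 0.6 × 0.5 × 0.0879 / 0.9 = 0.029 SD.
- High end (p = 0.20, b = 1, ρ = 0.9): E[π(1 − π)] = 0.1386; 0.9 × 1 × 0.1386 / 0.8 = 0.156 SD.

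**Simulation check.** 50 per arm, no true difference, 20,000 trials per cell. The likelihood estimate regresses month 12 on month 6 with a common slope. Type I error is that of the two-sided 5% available-case test.

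| p | ρ | Variance saved, random dropout | Bias, b = 0.5 in one arm | Bias, b = 1 in one arm | Type I error, b = 0.5 / b = 1 |
|---|---|---|---|---|---|
| 0.10 | 0.6 | 3.1% | 0.030 | 0.055 | 0.052 / 0.057 |
| 0.10 | 0.9 | 7.9% | 0.042 | 0.081 | 0.054 / 0.068 |
| 0.20 | 0.6 | 7.4% | 0.058 | 0.104 | 0.056 / 0.078 |
| 0.20 | 0.9 | 16.5% | 0.086 | 0.155 | 0.065 / 0.107 |

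Biases are absolute; the sign depends on which arm is affected and on the direction of the dependence. With month 6 in the model the bias was at most 0.002 SD in every one-arm cell. With b = 1 in both arms, the available-case bias was at most 0.003 SD and its type I error 0.047 to 0.052.

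**The case against.** The strongest reply is that the damaging scenario is not documented. After month 6 all patients receive open-label triheptanoin (Section 4.1), and the SAP gives no reason why measured caudate loss should drive dropout in one arm and not the other. Milder versions do little: at b = 0.5 the type I error stays between 0.052 and 0.065. Section 9 also reports reasons for withdrawal by arm, so a gross imbalance would be seen, and it declares secondary inference exploratory. All of this stands, and it limits the priority. It does not remove the loss of precision, which needs no differential dropout. Nor does it give a reason to prefer the weaker analysis when the scans and the software are already in the plan.

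A reader might draw stronger conclusions, which the SAP does not support:

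- *That the ANOVA is valid only if dropout is unrelated to outcome.* Equal dependence in both arms left the difference essentially unbiased.
- *That the bias can be read as a share of the trial's design effect.* Fifty per arm with 80% power at one-sided 0.025 implies (1.960 + 0.842) × √(2/50) = 0.56 SD, but for the 6-month placebo comparison. At 12 months the contrast is early against delayed start, for which the SAP states no target.
- *That all secondary results are affected to this degree.* Only cBSI was computed. The Pi/PCr index and the clinical scores already adjust for baseline, so their gain may be smaller.
- *That the month-6 scans are wasted altogether.* They supply the primary endpoint; they go unused only in the 12-month comparison.

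**Conclusion.** The point holds for 12-month cBSI as an inexpensive improvement of modest priority. Under assumptions the SAP neither states nor excludes (10–20% missing after month 6, correlation 0.6–0.9, 50 per arm), using month-6 cBSI reduces the variance by about 4–17% under random dropout. If dropout depends on month-6 loss in one arm only, at log-odds 0.5–1 per SD, it removes a bias of about 0.03–0.16 SD.

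The bias figures are conditional on that mechanism and do not predict what will happen in this trial. The correction relies on dropout being explained by observed data: it does not repair dropout that depends on the unseen month-12 value, and it recovers nothing for a patient with neither scan. The primary month-6 analysis is not affected.

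**What to change.** In Section 9, replace the 12-month cBSI ANOVA with one PROC MIXED repeated-measures model of month-6 and month-12 cBSI. Use arm, visit and arm-by-visit, unstructured covariance, Kenward-Roger degrees of freedom and a named simpler covariance structure in case of non-convergence. The adjusted version adds age, gender and BMI as now. Report the month-12 arm contrast from this model. Keep the month-6 primary analysis with its multiple imputation as it is, and keep the no-imputation rule for secondary criteria, with which the model is compatible.

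The same model with a baseline-by-visit term can serve the Pi/PCr index (M3, M6, M12) and the clinical scores. It need not extend to the diffusion and fibre metrics, where 27 regions × 6 metrics would mean 162 models.

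The cost is a change of SAP wording and a small amount of programming. No new data are needed, and both SAS 9.4 and PROC MIXED with Kenward-Roger are already planned. The downsides are a few more covariance parameters, the need for a convergence fallback, and the need to keep the rank-analysis fallback for non-normal data alongside the new model.
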